11 November 2021	7.0	
The following specific revisions made to the protocol sections are described below:
 
- The trial design is being changed from a randomized- controlled trial design to an open-label single arm trial design, therefore the following sections have been updated accordingly: Protocol/ CIP Synopsis, Section 1.3, 5, 6, 7.2, 7.3, 7.6, 10, 13.12 and 15- To reflect the change from randomized to an open-label trial, trial procedures and methods have been updated in Protocol/ CIP Synopsis, Section 8.1.1, 8.1.5, 8.1.18, 8.1.20, 8.1.21, 8.3.2 and 8.3.6. Methods was updated to include 3 Cohorts. Cohort #1 will not be part of the primary endpoint analysis

as these patients have already had follow-up visits as patients in the previous Control Arm. To harmonize all patients in the study, data for the primary endpoints will only be collected for patients who receive treatment from onset (i.e., Cohorts #2 and #3).

- Updating ISO 14155-2011 to the new version 14155:2020
 - Due to the fact that European sites are added to the trial the following sections have been updated to account for EU specific requirements:
 - o Added European Contact Details
 - o Adding Clinical Investigational Plan (CIP) throughout the document
 - o Adding Competent Authority (CA) and Independent Ethics Committee (IEC)), throughout the document
 - o Added section 8.1.4 on informing GPs
 - o Updated Adverse Event sections 9.1, 9.1.4, 9.2 and 9.3
 - o Added section 9.3.2 on Regulatory Reporting Requirements
 - o Added Appendix 14.7
 - Intended Use & Indications for Use have been revised in Protocol/ CIP Synopsis and section 1.4
 - Protocol/ CIP Synopsis, Section 6.2, 6.4 and 7.6 have been updated to reflect that the number of sites has been updated to 120 sites in the United States and Europe
 - Exclusion Criteria in Protocol/ CIP Synopsis and section 7.5 have been updated:
 - o Exclusion Criteria 19- to provide more clarity
 - o Added Exclusion Criteria 20 as per required by German Competent Authority (BfArM)
 - Section 1.2 and 15 have been updated to reflect recent updates and publications on Pulmonary Artery Pressure (PAP)
-

- Section 3.2 and 15 to update on the progress of all ongoing clinical trials at Endotronix
 - Additional secondary efficacy endpoints have been added to Protocol/ CIP Synopsis, section 5.1 and 10.4
 - o Added new Secondary Efficacy Endpoints # 3, # 4 and # 8
 - o Updated Secondary Efficacy Endpoints # 11

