The increasing acceptance of the clinical benefit of PAP guided HF management following the growing scientific evidence and acceptance by a variety of stakeholders has impacted enrollment in PROACTIVE-HF more than anticipated during the design of the study in late 2018. A randomized study design may still be possible from an academic standpoint, but in practice is growing exceedingly difficult and practically impossible. With increasing acceptance and utilization of PAP guided HF management, several clinicians have declined the study or refer some patients to commercial use of CardioMEMS, as they are hesitant to refer a patient to PROACTIVE-HF enrollment that may delay utilization of PAP guided HF management in the control arm when there is an approved PAP guided HF management (CardioMEMS) available to benefit the patient immediately outside of the study. This impact to enrollment has been further exacerbated by the COVID-19 pandemic, as clinicians and patients have been hesitant to accept the elevated risks of exposure to COVID-19 for a procedure that may not lead to benefit to a patient in the control arm for 12 months (at the time of cross-over to active treatment). A number of potential eligible study patients decided not to participate in PROACTIVE-HF as they were not willing to wait potentially for one year for therapy if the alternative commercial device is readily available. This issue may also lead to selection bias, as physicians may offer the study only to patients who they think can “wait” for PAP guided HF management, and therefore they are willing to randomize.

Taking the above-described recent advancements of PAP guided HF management into account and the subsequent negative impact on trial enrollment, an Open- Label Single Arm study design, will eliminate these concerns and allows all study subject prompt access to PAPGHFM treatment. A single arm study is well suited to show comparable effectiveness performance to the commercially available device and thus, will provide reasonable assurance that the device is effective for use in the intended population.

Single arm PROACTIVE -HF rationale

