5.1 Efficacy Endpoints

Primary Efficacy Endpoint through 6 months post- implant):

The primary efficacy endpoint is the 6 month incidence of HF related Hospitalizations or all-cause mortality.

Secondary Efficacy endpoints include:

1. Incidence of HF Hospitalizations or all-cause mortality at 12 months
2. Number of HF Hospitalizations at 6 and 12 months post-implant compared to the number of HF Hospitalizations in the 6 and 12 months prior to implant
3. Comparison of the number of HF Hospitalizations or Emergency Department/ Hospital Outpatient IV diuretic visits of Cohort #1 and Cohort #2+#3 at 6 and 12 month post implant
4. Change of NT-proBNP from Baseline through 6 and 12 months
5. Combined outcome of:
 - a. First and recurrent HF Hospitalizations
 - b. Emergency Department/ Hospital Outpatient IV diuretic visits
 - c. all-cause mortalityat 6 months, added together with equal weighting into a total number of events.
6. Heart failure hospitalization or Emergency Department / Hospital Outpatient IV diuretic visits at 6 and 12 month
7. Cardiac and all-cause mortality
8. Days Alive and Out of Hospital (DAOH)
9. IV diuretic visits
10. Heart failure related Medication changes
11. Change in PAP:

- a. From Baseline through 6 and 12 months in subjects with a baseline mPAP
 - i. above target range
 - ii. within or below target range
 - iii. overall
 - b. Before and after 6-Minute Walk Test
12. Percentage of device success as documented by ability of the System to successfully transmit PAP data
13. Patient Outcome Measures, measured by KCCQ
14. Functional status improvement, as measured by NYHA and 6-Minute Walk Test
15. Health Economic Analysis

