10.3 Primary Efficacy Endpoint and Hypotheses

To meet the objectives of the study, observed event rates in the single arm PROACTIVE-HF should be similar to observed event rates in the treatment arm of CardioMEMS studies. Furthermore, observed event rates in the single arm PROACTIVE-HF should be lower than observed event rates in the control arm of CardioMEMS studies.

Thus, we set the performance goal (PG) as the LOWER of 1) the meta-analysis upper bound confidence interval of CardioMEMS treated patients, and 2) the meta-analysis estimate of CardioMEMS control patients, further adjusted down by potential impact of SGLT2i.

Furthermore, we also require that the single arm PROACTIVE-HF observed event rate is LOWER than both 1) the meta-analysis estimate of CardioMEMS treatment patients, and 2) the lowest observed event rates of CardioMEMS control patients, further adjusted down by potential impact of SGLT2i.

The primary endpoint will be the 6 month incidence of HF related Hospitalizations (HFH) or all-cause mortality compared to a PG.

Meta-analysis of treatment and control event rates were considered in determining the Primary Endpoint PG. Meta-analyses were based on a random effects meta-analysis for the log-transformed

incidence rate fit via restricted maximum likelihood. Results are back transformed to the rate scale. Calculations were performed in R version 3.6.3 with the “metafor” package.

The mean 6 month event rate from the meta-analysis of prior control studies is 0.46, or 0.43 on an adjusted basis to account for SGLT2i inclusion in the guidelines^a. A 6 month event rate of 0.43 also represents a value just below both the highest event rate observed across the CardioMEMS treatment studies (0.44 in MEMS-HF) and the upper bound of the overall meta-analytic treatment estimate (0.44). Taking the totality of results from the meta-analysis of active treatment trials, individual results of active treatment trials, as well as the meta-analysis of control trials, we set the primary endpoint performance goal (PG₆) at 0.43.

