2.1	17-Aug-2023	[name]	
Repeated the primary safety analysis on ITT additionally. The cutoff for 6 month analysis updated to 180 days from 183 days
 
Added an AE summary for 'Other serious adverse events (AE) CEC adjudicated'
 
Added separate analyses of HFH and all-cause mortality from CEC adjudication results
 
The compression population update to Cohort #1, Cohort #2 and #3 from Cohort #1 and Cohort #2
 
The secondary endpoint #3 update to Comparison of the number of HF Hospitalizations or Emergency Department/ Hospital Outpatient IV diuretic visits of Cohort #1 and Cohort #2 + #3 at 6 and 12 months post implant from Comparison of the number of HF Hospitalizations or Emergency Department/ Hospital Outpatient IV diuretic visits of Cohort #1 and Cohort #2 at 6 and 12 months post implant
 
The secondary endpoint #14 Change from baseline in PAP parameters collected via CorPASS will not be performed for Cohort #1 population

This document is confidential.

I confirm that I have reviewed this document and agree with the content.

Approvals		
Syneos Health Approval		
[name], Biostatistician I	[name]	<small>Electronically signed by: [name] Reason: I am the author Date: Aug 17, 2023 14:58 GMT+8</small>
Lead Biostatistician	Signature	Date (DD-Mmm-YYYY)
[name], Principal Stat Programmer	[name]	<small>Electronically signed by: [name] Reason: I am the approver Date: Aug 17, 2023 10:28 GMT+2</small>
Lead Statistical Programmer	Signature	Date (DD-Mmm-YYYY)
[name], Assoc Dir, Biostatistics	[name]	<small>Electronically signed by: [name] Reason: I am the reviewer Date: Aug 17, 2023 17:52 GMT+8</small>
Senior Reviewing Biostatistician	Signature	Date (DD-Mmm-YYYY)
Endotronix, Inc.		
[name], Vice President Clinical Operations	[name]	<small>Electronically signed by: [name] Reason: I am the approver Date: Aug 17, 2023 09:11 GMT+2</small>
Sponsor Contact	Signature	Date (DD-Mmm-YYYY)

This document is confidential.

Table of Contents

Revision History	2
Approvals	3
1. Purpose.....	11
1.1. Responsibilities	11
1.2. Timings of Analyses.....	11
2. Study Objectives.....	12
2.1. Study Objective	12
2.2. Brief Description	12
2.3. Subject Selection.....	15
2.3.1. Inclusion Criteria.....	15
2.3.2. Exclusion Criteria.....	15
2.4. Determination of Sample Size.....	16
2.4.1. Primary Efficacy Endpoint (at 6 months post- implant).....	16

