4.6. Comparison Population

This population will include all implanted subjects from Cohort #1, Cohort #2 and #3. The Comparison Population will be used for analysis of secondary efficacy endpoint #3.

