All events until day x, which would be exact 6 or 12 months (180 or 365 days respective) post-implant visit would be summarized.

All events happened between day x and implant visit, which is exact 6 or 12 months (-180 or -365 days respective) pre-implant visit. Analysis will be done based on mITT population, PP population, and Cohort #1 population. Prior to the date of cut-off for the main analysis, it will be confirmed, if analysis based on PP population will be required.

This document is confidential.

7.1.6. Comparison of the number of HF Hospitalizations or Emergency Department/ Hospital Outpatient IV diuretic visits of Cohort #1 and Cohort #2 + Cohort #3 at 6 and 12 month post implant

The rate of mortality and HF hospitalizations or HF emergency department/hospital outpatient IV diuretic visits in each cohort at 6 or 12 month is calculated as the total number of observed events in each cohort divided by the (total observed exposure time/180 or 365) in each cohort from implant visit through 6 months or 12 months.

The information on mortality will be used as collected on the CRF, AE page with AE outcome = 'Death' or Study completion page with primary reason for discontinuation = 'Death'. The information on HF hospitalizations will be used as collected on the CRF, Hospitalization page, emergency department/hospital outpatient IV diuretic visits will be used as collected on the CRF, AE page with AEs resulted in = 'Emergency Department (ED) visit'/'Hospitalization'/'Urgent, unscheduled outpatient office/ practice' for AE categorized as 'Heart failure'.

The Cohort #1 and Cohort #2 + Cohort #3 subjects will then be compared with respect to rate of events per unit time using poisson regression. The test will be based on each subject's total number of events, treatment arm, and exposure time, where a subject's exposure is the time to death, early study discontinuation or 6 or 12 months, whichever is smaller.

Let λ_1 be the rate of events per 6/12 month on the Cohort #1 and let λ_2 be the rate of events per 6/12 month on the Cohort #2 + Cohort #3. The null hypothesis is $H_0: \lambda_1 \leq \lambda_2$ and the alternative hypothesis is $H_1: \lambda_1 > \lambda_2$.

The poisson regression calculation provides a one-sided p-value for the null hypothesis that the rate in the Cohort #1 is less than or equal to the rate in the Cohort #2 + Cohort #3.. The resulting p-values will be seen as explanatory.

```
proc genmod data = xxx;  
    class trt;  

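### Secondary endpoint #3 compares the former control arm only with Cohorts #2 and #3 pooled, and no Cohort #1 versus Cohort #2 rate ratio is planned

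*SAP*

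**What the plan says.** Protocol section 6 defines Cohort #1 as the former control arm, Cohort #2 as the former treatment arm and Cohort #3 as newly enrolled subjects. The protocol's amendment history for version 7.0 records the switch: "The trial design is being changed from a randomized- controlled trial design to an open-label single arm trial design".

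Secondary endpoint 3 in Protocol 5.1 concerns HF hospitalisations or emergency/outpatient IV diuretic "visits of Cohort #1 and Cohort #2+#3" at 6 and 12 months. SAP 4.6 builds the matching analysis set: "This population will include all implanted subjects from Cohort #1, Cohort #2 and #3". It adds: "The Comparison Population will be used for analysis of secondary efficacy endpoint #3".

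SAP 7.1.6 gives the method: "The Cohort #1 and Cohort #2 + Cohort #3 subjects will then be compared with respect to rate of events per unit time using poisson regression". Its model statement has a class variable `trt` and the log exposure offset, and nothing else. The alternative is one-sided (higher rate in Cohort #1), and the SAP treats the p-values as exploratory. Tables 14.2.2.3.1 to 14.2.2.3.6 all show Cohort #1 against #2+#3, overall, by sex and by ejection fraction, on site-reported and adjudicated events.

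For background only, the SAP revision history for version 2.1 notes: "The compression population update to Cohort #1, Cohort #2 and #3 from Cohort #1 and Cohort #2". That entry describes superseded text and is not a fault in itself.

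**The concern.** Cohorts #1 and #2 were formed by randomisation in the same enrolment phase. Cohort #3 was not randomised and came later. The protocol gives its own reasons to expect the two phases to differ:

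- **Background therapy.** Protocol 10.3 lowers the historical control rate from 0.46 to "or 0.43 on an adjusted basis to account for SGLT2i inclusion in the guidelines". The version 7.0 amendment that ended randomisation also added SGLT2 inhibitors to the Appendix 14.5 treatment guidelines.
- **Selection.** On the randomised design, Protocol 1.3 says: "This issue may also lead to selection bias, as physicians may offer the study only to patients who they think can" wait for pressure-guided care.
- **COVID-19.** Protocol 1.3 says that the pandemic made enrolment harder while there was a control arm.
- **Geography.** European sites are cited as an addition in version 7.0.

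A model with only a group term cannot separate these influences from a device effect. Endpoint #3 is also the only planned between-group test against care without pressure guidance, because the primary and first secondary tests use external performance goals. With no Cohort #1 versus #2 ratio planned, the least confounded comparison in the data has no estimate or interval.

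**Working it through.** **The plan's own figures.** No sample size or power is stated for endpoint #3. The nearest stated figure, power above 80% for the primary test, reproduces: an exact one-sample Poisson test with n = 406, 0.34 against 0.43 and one-sided 0.025 has critical count 148, attained alpha 0.022 and power 0.814. That is a different test and is not in question here.

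**Inputs**
- Cohort #1: up to 85 (protocol synopsis).
- Cohorts #2 + #3: 450 (Protocol 10.3).
- SGLT2i adjustment: 0.46 to 0.43 at 6 months (Protocol 10.3) and 0.75 to 0.70 at 12 months (Protocol 10.4).
- Assumption: Cohort #2 is about 85. Neither its size nor the allocation ratio is stated. Cohort #3 is then 450 − 85 = 365, and 365/450 = 0.811 of the pooled group.

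**Step 1. Drift with no device effect.** Let d be the rate factor acting on Cohort #3 only. The pooled ratio, #2+#3 over #1, is 1 − (365/450)(1 − d).
- 12 months: d = 0.70/0.75 = 0.933; ratio = 1 − 0.811 × 0.0667 = 0.946.
- 6 months: d = 0.43/0.46 = 0.935; ratio = 1 − 0.811 × 0.0652 = 0.947.
- With Cohort #2 between 60 and 170, the 6-month ratio runs from 0.944 to 0.959.

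**Step 2. Effect on the one-sided test at nominal 0.025.** With SE = sqrt(1/E1 + 1/E23), where E1 and E23 are the expected event counts in Cohort #1 and in #2+#3, the rejection probability is Φ(−ln(ratio)/SE − 1.96).
- 12 months: E1 = 85 × 0.75 = 63.75; E23 = 450 × 0.7094 = 319.2; SE = 0.137; Φ(0.0556/0.137 − 1.96) = 0.060.
- 6 months: E1 = 85 × 0.46 = 39.1; E23 = 450 × 0.4357 = 196.1; SE = 0.175; Φ(0.0543/0.175 − 1.96) = 0.050.
- A larger assumed drift of 0.80 at 6 months gives a ratio of 0.838 and rejection probability 0.168. Nothing in the documents supports that value; it only shows the sensitivity.

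**Step 3. Precision of the two contrasts at 12 months.** This uses 0.633 and 0.525, the HF hospitalisation rates quoted from GUIDE-HF in Protocol 1.2. They are stand-ins: endpoint #3 counts a broader event.
- 85 vs 450: sqrt(1/(85 × 0.633) + 1/(450 × 0.525)) = 0.151.
- 85 vs 85: sqrt(1/(85 × 0.633) + 1/(85 × 0.525)) = 0.202, before any cut at unblinding.
- Power at one-sided 0.025 for 0.46 against 0.38 to 0.34 is about 12% to 23% (85 vs 85) and 19% to 39% (85 vs 450).

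**Step 4. Contamination of Cohort #1.** The synopsis and Protocol section 6 have clinicians start managing Cohort #1 to target pressures once unblinded. Note 13 to the Protocol 14.1 schedule places unblinding at the month 12 visit or at cross-over, whichever is earlier. SAP 5.2 and 7.1.6 end exposure at death, discontinuation or 6/12 months, never at unblinding. Controls who crossed over before month 12 therefore contribute pressure-guided time to the control rate, which pulls either contrast towards no difference.

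**The case against.** The SAP matches the protocol's endpoint: #1 against #2+#3 is what Protocol 5.1 and 10.4 list. The result is exploratory, and study success rests on the performance goal.

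A reader might infer that the plan attributes any fall in event rates to the device. The documents do not say so: nowhere is endpoint #3 credited to the device or used for a claim. A reader might also infer that the randomised comparison is hidden. It is not. SAP 5.1 summarises Cohorts #2 and #3 separately, SAP 4.5 reports Cohort #1 on its own, and Tables 14.2.2.6.1 and 14.2.2.6.5 give closely related event counts, so crude rates can be set side by side. Only the ratio and its interval are missing.

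The 0.946 is not an estimate of the change between cohorts. The 0.933 factor adjusts historical studies to an assumed 50% SGLT2i use, and the version 7.0 guideline update reaches Cohorts #1 and #2 as well. Applying all of it to Cohort #3 alone is close to an upper bound for that mechanism.

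The strongest point concerns total error. Taking the illustrative bias at face value, the pooled contrast has root mean square error sqrt(0.056² + 0.151²) = 0.161, below the 0.202 of the randomised contrast.

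All of this stands. It argues against replacing the pooled contrast, not against adding the randomised one.

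**Conclusion.** The point holds as a modest improvement to an exploratory secondary analysis. Endpoint #3 as planned cannot separate device effect from enrolment period and selection, and no Cohort #1 versus #2 rate ratio or CI is planned. Under the stated assumptions, the sponsor's own therapy adjustment alone would produce a ratio of about 0.946 and raise the one-sided error from 0.025 to about 0.050 to 0.060. The net direction is uncertain: selection and COVID-19 could act either way, and cross-over of controls pulls towards no difference.

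Two stronger readings are not supported. First, Cohort #1 versus #2 is not free of bias by design: it is a clean randomised contrast only before Cohort #1 is unblinded. Second, it should not become the lead contrast from which a device effect is concluded. It is less precise, has low power, and is not the contrast that the protocol lists. The primary endpoint and the gatekept 12-month endpoint are unaffected.

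**What to change.** In SAP 7.1.6 and Tables 14.2.2.3.1 to 14.2.2.3.6:

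1. Replace the two-level `trt` with a three-level cohort factor in the same Poisson model.
2. Add the Cohort #1 versus Cohort #2 rate ratio with 95% CI as a supportive randomised contrast. End Cohort #1 follow-up at unblinding to PAP and apply the same calendar cut to Cohort #2.
3. Show Cohort #3 separately.
4. Keep Cohort #1 versus #2+#3 as the protocol-listed contrast, labelled non-randomised and non-concurrent.
5. Record the addition in SAP section 10.

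The cost is SAP wording, a derived cut date and extra table rows; no new data are needed and no protocol endpoint is removed. The downside is imprecision: the SE of the log rate ratio is about 0.20 against 0.15 at 12 months with 85 per arm assumed, and larger once follow-up is cut. The added contrast should be presented as an estimate with its interval, not as a test.

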4.7. Protocol Deviations

Sponsor will assess the protocol deviations as minor or major and provide this information to Syneos Health prior to date of cut-off, main analysis, and prior to database lock for the follow-up (final) analysis.

This document is confidential.

5. General Aspects for Statistical Analysis

5.1. General Methods

- Unless otherwise specified, summaries will be presented by cohort (cohort #2 vs cohort #3) and overall
- Continuous variables will be summarized using the number of observations (n), mean, standard deviation (SD), median, minimum, and maximum. Categorical variables will be summarized using number of observations (n), frequency and percentages of subjects.
- All relevant subject data will be included in listings. All subjects entered into the database will be included in subject data listings, except screen failures. A separate listing will present the screen failures along with the inclusion criteria they failed and/or exclusion criteria they met. All listings except 16.2.3.x will be repeated for Cohort #1 population.
- In case of multiple assessments at a given time point (planned, repeat, unscheduled) the planned visit will be used for the analysis. For the definition of the baseline value, the last available value (e.g. unscheduled) prior to implant of Cordella PA Sensor will be used.

5.2. Key Definitions

Age

Age at screening is derived in the database and this value will be used for all analyses.

Definition of Baseline for safety assessments

Baseline will be defined as the last available value prior to the implant of Cordella PA Sensor and may be at any visit between Screening (V1) and Cordella PA Sensor Implant Visit (V2).

Definition of Baseline for PAP measurements

Baseline will be defined as value at Implant Visit (V2) obtained before discharge .

Change from Baseline

Absolute change from baseline:

Absolute change = Post-baseline value –baseline value

Time to Onset of AE

Time to onset of AE [days] = Date of start of AE – Date of implant of Cordella PA Sensor + 1

Start Day of concomitant medication

If medication starts before date of implant of Cordella PA Sensor:

Start Day of Medication = Date of start of medication – Date of implant of Cordella PA Sensor

If medication starts at/after date of implant of Cordella PA Sensor

Start Day of Medication = Date of start of medication – Date of implant of Cordella PA Sensor + 1

Incomplete start dates of medication will not be imputed. Start day of medication will be missing.

Stop Day of concomitant medication

If medication stopped before date of implant of Cordella PA Sensor:

Stop Day of Medication = Date of end of medication – Date of implant of Cordella PA Sensor

If medication stops at/after date of implant of Cordella PA Sensor

This document is confidential.

Stop Day of Medication = Date of end of medication – Date of implant of Cordella PA Sensor + 1
Incomplete end dates of medication will not be imputed. Stop day of medication will be missing.

Definition of study completed/discontinued/ongoing

A subject will be defined as study ‘completed’/‘discontinued’ based on the eCRF information. At the time of the pre-defined main analysis, subjects which are ongoing at date of cut-off will be counted as ‘ongoing’.

Time since first diagnosis of heart failure

Time since diagnosis [months] = ((Date of Screening – Date of first HF diagnosis)+1)/30

Exposure time:

which would be exact 6 or 12 months (180 or 365 days respective) post-implant visit for subjects who are still in the study at/after this timepoint.

which would be [date of last available date – date of Implant visit + 1] for subjects who withdraw from study prior to month 6 or 12 (180 or 365 days respective) post-implant visit.

